1 INTRODUCTION

Following the Food and Drug Administration (FDA) approval of certolizumab pegol (Cimzia®) for Crohn's disease (CD), UCB has committed to collect additional long-term, post-marketing safety data on patients exposed to the product in a real-life setting. To achieve this goal, a pharmacoepidemiologic study entitled SECURE was designed. The study began in January 2009 with the goal of collecting prospective data on 2000 patients prescribed Cimzia and a 2000 patient comparator group prescribed other treatments (including biologics) for CD.

The protocol has been amended (Amendment 5) to cease enrolling patients into the SECURE registry (protocol C87075). The decision was based on the results of a current interim analysis that indicated that no new safety issues had emerged from the currently known safety profile of Cimzia. Patients who already enrolled in C87075 at the time of discontinuation will continue to be followed.

The SECURE registry represents a significant addition to post-marketing safety assessments based on spontaneous reports. The study is anticipated to continue monitoring all enrolled patients for approximately 8 years after enrollment. Section 14 provides detailed information on protocol history since Final Version.

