5 ADVERSE EVENTS OF INTEREST, SERIOUS ADVERSE EVENTS, CASE AND EXPOSURE DEFINITIONS

Serious adverse events and AEs of interest are the focus of this registry; Investigators are not expected to enter nonserious AEs in the eCRF except for AEs of interest regardless of seriousness.

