6.4.2 Secondary Analyses

Descriptive statistics on the Investigator's assessment of disease at study entry will be presented. Disease severity, measured by Investigator's and patient's assessment, will be used to quantify the potential influence of disease severity on the safety profile. Demographics and baseline patient characteristics, including medical history, CD history, physical examination findings (if available), vital signs (if available), the HBI score, patient's assessment, and reasons for treatment and study discontinuation will be summarized. Concomitant medications will be presented following the World Health Organisation Drug (WHO Drug)

classification. Characteristics of treatment with Cimzia or other medication such as planned treatment duration and actual duration of therapy will be tabulated. A stratified analysis by cumulative Cimzia exposure may also be performed for malignancy events to identify potential patterns in long-term use of Cimzia.

All AEs will be summarized descriptively by MedDRA Primary System Organ Class and Preferred Term (latest version at each interim analysis). Each interim analysis will indicate the MedDRA version that was utilized. Additional tables will summarize those AEs by severity and relationship to study drug as well as separate tables for AEs leading to withdrawal from the study, SAEs and deaths.

Further details on all analyses will be provided in the SAP.

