9.3 Other Adverse Events

Other adverse event for both Cimzia and Control arms will be collect through the registry according to the judgment of the Investigator.

Change #18

9.4 Case Definition:

Cimzia Case:

Cases will be attributable to Cimzia identified by two methods. The first method will assume a case will be attributable to Cimzia after the first dose of the medication regardless of medication discontinuation and time to onset of disease. The second method will be a series of sensitivity analyses and stratifications to evaluate different clinically driven definition of cases attributable to drug. Specifics on data handling guidelines for managing missing or partial data will be documented in the SAP.

Control Case:

Cases will be attributable to non-Cimzia medications identified by two methods. The first method will assume a case will be attributable to the non-Cimzia medication after the first dose of the medication regardless of medication discontinuation and time to onset of disease. The second method will be a series of sensitivity analyses and stratifications to evaluate different clinically driven definition of cases attributable to drug. Specifics on data handling guidelines for managing missing or partial data will be documented in the SAP.

Has been changed to:

9.3 Case Definition:

Cimzia Case:

Cases will be attributable to Cimzia identified by two methods. The first method will assume a case will be attributable to Cimzia after the first dose of the medication regardless of medication discontinuation and time to onset of the event. The second method will be a series of sensitivity analyses and stratifications to evaluate different clinically driven definition of cases attributable to drug. Specifics on data handling guidelines for managing missing or partial data will be documented in the Statistical Analysis Plan (SAP).

Control Case:

Cases will be attributable to non-Cimzia medications identified by two methods. The first method will assume a case will be attributable to the non-Cimzia medication after the first dose of the medication regardless of medication discontinuation and time to onset of the event. The second method will be a series of sensitivity analyses and stratifications to evaluate different clinically driven definition of cases attributable to drug. Specifics on data handling guidelines for managing missing or partial data will be documented in the SAP.

Change #19

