- Any changes in medication
- Any administrative changes such as change in contact information

Change #9 Section 9 Adverse events of interest, serious adverse events, case and exposure definitions

New text added –

Although serious adverse events and nonserious adverse events of interest are the focus of this registry, Investigators are expected to enter all AEs in the eCRF.

Change #10 Section 9.2 Adverse events of interest

New text (final bullet) –

- Other events:
 - Congestive heart failure
 - Aplastic anemia, pancytopenia, thrombocytopenia, neutropenia and leucopenia
 - Serious bleeding events
 - Serious skin reactions (eg, Stevens Johnson Syndrome, toxic epidermal necrosis, and erythema multiforme)

Change #11 Section 9.3 Anticipated serious adverse events (new section)

New text -

The following list of Anticipated SAEs has been identified as these events are anticipated to occur in the population studied in this protocol at some frequency that is independent of drug exposure. This original list will remain in effect for the duration of the protocol.

This list does not change the Investigator's obligation to report all serious AEs (including Anticipated SAEs) as detailed in Section 9.7.

Crohn's disease
perianal abscess
abdominal pain

Change #12 Section 9.5 Exposure definition

Old text -

Cimzia Exposure:

Cimzia exposure will be calculated by two methods. The first method will assume exposure from day one of the first dose of Cimzia medication regardless of medication discontinuation through the date of the last follow-up evaluation. The second method will be a series of

sensitivity analyses and stratifications to evaluate the different clinically driven definitions of exposure to drug. Specifics to these definitions will be outlined in the SAP.

Control Exposure:

Non-Cimzia® medication exposure will be calculated by two methods. The first method will assume exposure from day one of the first dose of the non-Cimzia® medication regardless of medication discontinuation through the date of the last follow-up evaluation. The second method will be a series of sensitivity analyses and stratifications to evaluate the different clinically driven definitions of exposure to drug. Specifics to these definitions will be outlined in the SAP.

Has been changed to –

Cimzia Exposure:

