As this is a 10-year follow up registry study, the technologies used for this registry such as EDC will be 21 CFR Part 11 compliant and evaluated on an on-going basis throughout the registry study to ensure upgrades are made when necessary.

Change #15

Section 8.8.1, Enrollment Visit

The reference to “Crohn’s Disease” was replaced by the abbreviation “CD”

Change #16

Section 8.8.2, Follow-Up Period

OLD TEXT:

The following data will be collected by the enrolling physician in EDC at each follow-up interval:

- All SAEs and nonserious AEs of interest that have been reported since last follow-up
- Investigator’s HBI completed at clinic visits or modified HBI completed during telephone contacts. This may also be completed by qualified site personnel as designated by the Investigator.
- Investigator’s assessment of disease severity
- Full details on exposure (e.g., dose, frequency) to Cimzia or other medication
- Any changes in medication
- Reasons for discontinuation of Cimzia and/or other medication for Crohn’s disease

NEW TEXT:

The following data will be collected as available by the enrolling physician in EDC at each follow-up interval:

- All SAEs and AEs of interest that have been reported since last follow-up
- Investigator’s HBI completed at clinic visits or modified HBI completed during telephone contacts. This may also be completed by qualified site personnel as designated by the Investigator
- Investigator’s assessment of disease severity
- Full details on exposure (eg, dose, frequency) to Cimzia or other medication
- Any changes in medication
- Reasons for discontinuation of Cimzia and/or other medication for CD

Change #17

Section 9, Adverse Events of Interest, Serious Adverse Events, Case and Exposure Definitions

OLD TEXT:

Although serious adverse events and nonserious adverse events of interest are the focus of this registry, Investigators are expected to enter all AEs in the eCRF.

NEW TEXT:

Serious adverse events and AEs of interest are the focus of this registry; Investigators are not expected to enter nonserious AEs in the eCRF.

Change #18

Section 9.1, Definitions; last paragraph

OLD TEXT:

All Serious Adverse Events (of interest or other) must be reported within 24 hours of being acknowledged by the Investigator.

NEW TEXT:

All SAEs must be reported within 24 hours of being acknowledged by the Investigator.

Change #19

Section 9.2, Adverse Events of Interest

OLD TEXT:

- Other events:
 - Congestive heart failure

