2.3 Study design and conduct

Following protocol amendment 5, this long-term observational study in the USA stopped enrollment with approximately 3045 patients enrolled since study start. From the original study design, approximately half of enrolled patients will be receiving Cimzia for ≤ 12 months or about to receive Cimzia at the time of enrollment. The study will be conducted in all regions in the USA at approximately 280 enrolling investigative sites (community based and academic practice).

Recruitment of Cimzia-treated and comparator patients will be monitored and controlled as needed, and to ensure balanced enrollment over time between both cohorts, recruitment will be matched for disease severity (mild/moderate/severe), age categories and gender.

Patients will be followed for approximately 8 years (reduced from 10 years in protocol amendment 5) during normal physician visits and through direct patient follow-up in the form of web, mail surveys and/or phone follow-up calls. All patients will receive and use their medications according to their normal course of medical treatment per physician clinical judgment.

Follow-up data on the patients will be reported by physicians approximately every six months following enrollment while direct patient follow-up data will be collected quarterly via internet, mail or telephone.

Quarterly progress reports will be generated and sent to the FDA during the patient enrollment period. Subsequently, more detailed yearly informal interim analyses may be conducted to provide updates for regularly scheduled steering committee meetings or to the FDA on the information collected in this study. As agreed with FDA, the study is ending on 28 August 2020, and a single final study report will be submitted in 2021.

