8.2.2 Adverse Events

Any event reported by the investigator or found in the drug safety database excerpt is considered an adverse event. Investigator and drug safety AEs have been reconciled by the study physician to avoid over reporting.

When an AE is considered serious in either source, it is treated as serious in the analysis and the related coding data is used.

Events reported in the patient survey are not considered confirmed AEs and are excluded from the analysis.

AE tabulations will be done using malignancy rules (for malignancies) separately using acute event rules (all AEs) unless otherwise specified.

A summary of study-emergent AEs, including the number of events reported, the number and percentage of patients reporting at least one AE, the number and percentage of patients reporting at least one AE of Interest, the number and percentage of patients with at least one serious AE (SAE), and the number and percentage of deaths will be presented. In addition, the number and percentage of patients reporting at least one study-emergent treatment-related AE, the number and percentage of patients reporting at least one study-emergent treatment-related AE of Interest, and the number and percentage of patients with at least one study-emergent treatment-related SAE will also be reported. AE summaries will be produced on the enrolled cohort as well as the malignancy/acute event rules.

Study-emergent AEs are those which first occur or increase in relationship to treatment after the first dose of any CD drug following enrollment.

A breakdown of the number and percentage of patients reporting each AE as well as the number of AEs, categorized by SOC, HLT, and PT coded according to MedDRA, will be presented. Note that patients are only counted once within each SOC, HLT, or PT. Uncoded AEs will be summarized in unknown SOC, HLT and PT. This will be produced for the enrolled cohort as well as both the malignancy and acute event rules.

A further tabulation of these data, broken down by relationship to treatment, will be presented. Patients with multiple events within a particular body system or preferred term will be counted under the category of their most drug-related event within that SOC, HLT or PT. Relationship to treatment is categorized as related or not related as collected on the eCRF.

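### SAP 8.2.2 pools nonserious AEs over eras with different collection rules, so their frequencies cannot be read as incidence

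*SAP*

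**What the plan says.** The analysis side is broad. SAP 8.2.2 counts as an AE any event reported by the investigator or found in the drug safety database excerpt, and plans "A breakdown of the number and percentage of patients reporting each AE as well as the number of AEs" by SOC, HLT and PT. It adds an overall summary (any AE, any related AE), a table by relationship and a table for patients with multiple occurrences. These are produced by enrollment cohort or under the exposure rules, with no restriction by protocol era and no caveat. Protocol 6.4.2 is equally broad: "All AEs will be summarized descriptively by MedDRA Primary System Organ Class and Preferred Term". SAP 8.2.3 takes hepatic events, which it says are not officially AEs of interest, from all TEAEs.

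The collection side is narrower and changed over time. For nonserious AEs not of interest, the amendment history in Protocol 14 shows:

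- Original protocol (section deleted by Amendment 1, Change #17): other AEs "will be collect through the registry according to the judgment of the Investigator".
- Amendment 1: the registry asks for SAEs and nonserious AEs of interest.
- Amendment 2, Change #9: "Investigators are expected to enter all AEs in the eCRF".
- Amendment 3, Change #17: "Investigators are not expected to enter nonserious AEs in the eCRF".
- Current Section 5: "Investigators are not expected to enter nonserious AEs in the eCRF except for AEs of interest regardless of seriousness".

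The history is used here only to establish which rule governed data that the final analysis pools. A difference between the log and the current text is not the complaint.

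**The concern.** A percentage of patients with a given AE is read as how often that AE occurred. Here the denominator is all patients over all years. For nonserious events not of interest, the numerator was asked of every site in only one short stretch. A patient enrolled in 2010 passed through that stretch. A patient enrolled in 2015 did not, yet sits in the same denominator.

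The only calendar-time device in the SAP is calendar year of enrollment, in the covariate lists of 4.1 and 8.1.2. It serves the propensity and regression models, does not enter the 8.2.2 tables, and does not date the person-time. The tables at stake are any AE, related AE, multiple occurrences, SOC/HLT/PT, and nonserious hepatic events.

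**Working it through.** The plan states no figure for this point, so there is none to reproduce.

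**Step 1: length of each era.** Dates come from Protocol 14.1 Change #1 and 14.3 Change #2; the end date is from SAP 2.3 ("As agreed with FDA, the study is ending on 28 August 2020"). The clock starts at the original protocol date, consistent with "The study began in January 2009" in Protocol 1. Years = days / 365.25.

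| Era | Rule for nonserious AEs not of interest | Days | Years |
|---|---|---|---|
| 06-Jan-2009 to 24-Jun-2009 | investigator judgment (endpoint text then in force spoke of all AEs) | 169 | 0.46 |
| 24-Jun-2009 to 05-Dec-2011 | not requested | 894 | 2.45 |
| 05-Dec-2011 to 04-Dec-2013 | expected | 730 | 2.00 |
| 04-Dec-2013 to 28-Aug-2020 | not expected | 2459 | 6.73 |
| Total | | 4252 | 11.64 |

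Share of calendar time in the window: 730 / 4252 = 17.2%. Counting the ambiguous first era as well: (730 + 169) / 4252 = 21.1%, or 2.46 years.

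**Step 2: share of one patient's follow-up in the window**, if followed to 8 years or study end:

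- enrolled mid-2009 to mid-2011: 2.0 / 8.0 = 25%
- enrolled mid-2012: 1.42 / 8.0 = 18%
- enrolled mid-2013: 0.42 / 7.16 = 6%
- enrolled after 04-Dec-2013: 0%

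**Step 3: share of all patient time in the window.** For entry time e, expected time in the window is [exp(−λ(a−e)) − exp(−λ(b−e))] / λ. Here a is the later of entry and window start, b is the earliest of window end, e + 8 years and study end, and λ = −ln(0.92), from the planning drop-out of 8% a year. The documents do not give the enrolment curve, so two shapes are assumed. Uniform entry to March 2017 gives 15.9%. Uniform entry over the first 5 years gives 23.2%.

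**Step 4: effect on a pooled frequency.** Let s be the share of time in the window and f the completeness of reporting outside it. Assume full reporting inside the window and a constant true rate. The fraction of nonserious AEs captured is c = s + f(1 − s). The documents give no value of f, so a range is shown.

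| Patients | s | f = 0 | f = 0.25 | f = 0.50 |
|---|---|---|---|---|
| All, entry uniform to March 2017 | 0.16 | 0.16 | 0.37 | 0.58 |
| All, entry uniform over 5 years | 0.23 | 0.23 | 0.42 | 0.62 |
| Enrolled mid-2009 to mid-2011 | 0.25 | 0.25 | 0.44 | 0.63 |
| Enrolled after 04-Dec-2013 | 0 | 0 | 0.25 | 0.50 |

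At the same true rate, early entrants therefore show 0.4375 / 0.25 = 1.75 times the frequency of late entrants at f = 0.25, and 0.625 / 0.50 = 1.25 times at f = 0.50. This is a contrast between enrolment dates, not between treatments.

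**Step 5: treatment groups.** The same formula would give a Cimzia/comparator distortion only if s were known for each group's on-drug time. No document gives the calendar dates or durations of exposure by group, so the calculation stops here.

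**The case against.** The strongest reply is that the outputs that matter are already protected. SAEs were to be reported in every era. SAP 8.2.4 repeats the tables for SAEs, AEs of interest have their own analyses, and malignancy is the primary outcome. Everything is declared descriptive, and the table shells and the Analysis Data Reviewers Guide, where a caveat might sit, are not public. This limits the reach of the point but does not remove it: a descriptive table should describe occurrence, not the reporting instruction.

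The eras are also less sharp than the dates suggest. Amendment dates are not site implementation dates. Amendment 2's own schedule, follow-up data list and endpoint text still asked only for SAEs and nonserious AEs of interest. A reader might infer that collection was complete in the window and forbidden afterwards. The texts say only expected and not expected. This blurs the edges without making the pooled counts comparable.

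A reader might also infer that the tables are biased against Cimzia, because Cimzia time comes early in follow-up while comparator time runs on. The documents do not support that:

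- Under SAP 3.2.1.2 and 3.2.1.3, acute-rule comparator time also stops, at last dose plus 7, 28 or 70 days, and untreated time goes to a separate Gap group.
- Several SAP Appendix 1 scenarios have Cimzia starting after comparator.
- With similar entry dates and equal on-drug durations in both groups there is no distortion, and reversing which group stays on drug longer reverses its direction.
- For the enrollment-cohort tables, Protocol 4.2 aimed at balanced enrollment over time, which would tend to equalise the window shares.
- SAP 8.2.2 plans counts and percentages of patients, not rate ratios, and no table of all AEs by time on drug.

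**Conclusion.** The point holds for absolute frequencies. Entry of nonserious AEs not of interest was expected of all sites for about 2.0 of 11.6 years (17%), or at most about 2.5 years (21%), while SAP 8.2.2 and the hepatic-event summary in 8.2.3 pool all years. Those frequencies depend on when patient time fell and cannot be read as incidence. The share of patient time in the window, about 16% to 23%, rests on assumed enrolment shapes and the planning drop-out. The captured fractions also rest on assumed completeness outside the window.

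A distortion between Cimzia and comparator is possible, but its direction and size are unknown and no rate ratio should be attached to it. SAE tables and the malignancy outcome are largely unaffected.

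**What to change.** In SAP 8.2.2, base the whole-study AE tables on SAEs, plus AEs of interest counted from the amendment at which each category joined the list. The start date is needed because the list grew: acute hypersensitivity reactions and, by name, solid malignancies at Amendment 1; heart failure, cytopenias, serious bleeding and serious skin reactions at Amendment 2.

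Put other nonserious AEs, and nonserious hepatic events from 8.2.3, in a separate table split into before Amendment 2, Amendment 2 to 3, and after Amendment 3, each with its own person-time. Keep the full AE listing that 8.2.2 already plans, so no reported event is lost. Footnote the collection rule by amendment, and state that site implementation may lag the amendment dates.

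The cost is SAP wording, a date flag in the AE programs and one extra table. The price is less pooled detail on nonserious events. No new data are needed.

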8.2.3 Adverse Events of Interest

The AEs of interest and the approach for summarizing them is briefly described below. Further information is provided in the guidance document (AEs of Interest – Cimzia Program 2018-01-05).

- Serious infections, including opportunistic infections. Serious infections will be summarized using the Serious TEAE table. In addition, opportunistic infections (including tuberculosis) will be presented in a table using UCB-defined search criteria.
- Malignancies, including lymphoma. These will be presented in 2 tables using the Standardized MedDRA Query (SMQ) criteria “Malignant or unspecified tumours” and “Malignant tumours” respectively.
- Serious cardiovascular events (also called major adverse cardiac events or MACE). These will be presented in a table including all serious TEAEs with the SMQs of “Haemorrhagic central nervous system vascular conditions”, “Conditions associated with central nervous system haemorrhages and cerebrovascular accidents”, and “Ischaemic central nervous system vascular conditions” with the exception of events coding to a PT of “Transient ischaemic attack”, including all serious TEAEs with the HLT of “Ischaemic coronary artery disorders” except events coding to PTs of “Chest Pain” or “Chest discomfort” and including all serious TEAEs with HLTs of “Heart Failures NEC”, “Left Ventricular Failures”, or “Right Ventricular Failures” and which also code to the SOC of “Cardiac Disorders”.
- Congestive heart failure. These will be manually identified by the study physician from the TEAE table.
- Demyelinating-like disorders will be presented in table which is based on the SMQ = “Demyelination”. The SMQ search should include all TEAEs which code to a PT included in Scope=Narrow group within the SMQ. TEAEs which code to a PT included in the Scope=Broad group within the SMQ should be excluded from the search.
- Aplastic anemia, pancytopenia, thrombocytopenia, neutropenia, and leucopenia. These will be presented in a table using the criteria SMQ = “Haematopoietic cytopenias” in the subset of Serious TEAEs.
- Serious bleeding events. These will be presented in a table using the criteria SMQ = “Haemorrhage terms (excl laboratory terms)” in the subset of Serious TEAEs.
- Lupus and lupus-like illness. These will be manually identified by the study physician from the TEAE table.

- Serious skin reactions (eg, Stevens-Johnson Syndrome, toxic epidermal necrosis, and erythema multiforme). These will be manually identified by the study physician from Serious TEAE table.

Although not officially AEs of interest, the following events will also be summarized as described in the AEs of Interest – Cimzia Program 2018-01-05 guidance document.

- Hepatic events. These will consist of a subset of all TEAEs, identified using the following 5 SMQs: Cholestasis and jaundice of hepatic origin; Hepatic failure, fibrosis, and cirrhosis and other liver damage-related conditions; Hepatitis, noninfectious; Liver-related investigations, signs and symptoms; and Liver-related coagulation and bleeding disturbances.
- Hypersensitivity reactions and anaphylactic reactions. Hypersensitivity reactions will be summarized as any TEAEs occurring on the same day or the day after injection was received, which code to the following preferred terms: Administration site hypersensitivity, Documented hypersensitivity to administered product, Drug hypersensitivity, Hypersensitivity, Hypersensitivity vasculitis, Infusion site hypersensitivity, Injection site hypersensitivity, Medical device site, hypersensitivity, Type II hypersensitivity or Type IV hypersensitivity reaction. Anaphylactic reactions will be defined using an algorithmic approach as described in the “AEs of Interest – Cimzia Program 2018-01-05” guidance document.
- Specific to study and not from the “AEs of Interest – Cimzia Program 2018-01-05” guidance document, we will also look at Malignant Lymphomas using the Narrow PTs from the “Malignant Lymphomas” SMQ, and into Autoimmune disorders and Lupus/Lupus-Like syndromes.
- Specific to study and not from the “AEs of Interest – Cimzia Program 2018-01-05” guidance document, we will also look at cases of non-melanoma Skin Cancer. These will be manually identified by the study physician from the TEAE table.

Table 8.1: Overview of malignancy events and acute events in this study

Overview of Events	
Event	Event Type (Malignancies are in addition analyzed following acute rules)
Malignant or unspecified tumor	Malignancy
Malignant tumor	Malignancy
Non melanoma skin cancer	Malignancy
Malignant Lymphoma	Malignancy
Serious infection	Acute
Opportunistic infection	Acute
Serious cardiac event	Acute
Congestive heart failure	Acute
Demyelinating-like disorder	Acute
Aplastic Anemia	Acute
Serious bleeding	Acute
Lupus and Lupus-like illness	Acute

Serious skin reaction	Acute
Hepatic event	Acute
Hyper/Anaphylactic reaction	Acute
Autoimmune Disorder	Acute

